PPV - Positive Predictive Value

PRO - Patient Reported Outcomes

SAP - Statistical Analysis Plan

SC - Steering Committee

This document contains information that is privileged or confidential and may not be disclosed unless such disclosure is required by applicable laws and regulations. The information in this document is the property of Apple Inc. and may not be reproduced, published, or disclosed to others without written authorization from Apple Inc.

PROTOCOL SYNOPSIS

Study Title	Apple Heart Study 1.2: evaluation of the use of the Apple Watch for identification of cardiac arrhythmias
Protocol Version	1.14
Protocol Date	November 13, 2018
Study Design	Prospective, single arm, experimental, non-significant risk study.
Inclusion Criteria	
 1. Possession of the following at time of eligibility screening, ascertained from automatic hardware/software/device pairing check: 
 I. iPhone (5s or later) with iOS version 12.1.1 or later defined as iPhone model/iOS version used to complete screening eligibility. II. Apple Watch (Series 1-4) with watchOS version 5.1.2 or later defined as Apple Watch model/watchOS paired with iPhone used to complete screening eligibility. 2. At least one of the following by self-report before consent: 
 I. Irregular Rhythm Notification II. ECG app classification of Atrial Fibrillation III. ECG app classification of Inconclusive defined as “Inconclusive,” “Heart Rate Over 120,” or “Heart Rate Under 50” 3. Age \geq 22 years at time of eligibility screening, ascertained from self-reported date of birth. 4. Current resident of the United States at time of eligibility screening, defined by self-reported state of residence within the 50 states of the United States or District of Columbia, and will reside in the United States for the length of the study. 5. Proficient in written and spoken English, defined by self-report of comfort reading, writing, and speaking English on iPhone. 6. Valid phone number associated with iPhone, ascertained from self-report. 7. Valid email address, ascertained from self-report.

This document contains information that is privileged or confidential and may not be disclosed unless such disclosure is required by applicable laws and regulations. The information in this document is the property of Apple Inc. and may not be reproduced, published, or disclosed to others without written authorization from Apple Inc.

Exclusion Criteria	
1. Shared iCloud account2. Shared AppleWatch
---------------------------	---

This document contains information that is privileged or confidential and may not be disclosed unless such disclosure is required by applicable laws and regulations. The information in this document is the property of Apple Inc. and may not be reproduced, published, or disclosed to others without written authorization from Apple Inc.

	
Objectives
 
1a. To measure the proportion of participants with an Irregular Rhythm Notification (IRN) prior to enrollment who have atrial fibrillation or atrial flutter (AF) confirmed by ambulatory electrocardiographic (ECG) patch monitoring.1b. To measure the proportion of participants with an ECG app classification of Atrial Fibrillation (ECG app-AFib) prior to enrollment who have AF confirmed by ambulatory ECG patch monitoring.2a. To measure the proportion of participants who receive an IRN or ECG app-AFib reporting contact with a non-study healthcare provider at 15 and 60 days after study enrollment.2b. To measure the proportion of participants with an ECG app classification of inconclusive prior to enrollment who have AF confirmed by ambulatory ECG patch monitoring.2c. To measure the proportion of participants who have AF confirmed by ambulatory ECG patch monitoring by age at enrollment (< 65 and 65+).
--	--

This document contains information that is privileged or confidential and may not be disclosed unless such disclosure is required by applicable laws and regulations. The information in this document is the property of Apple Inc. and may not be reproduced, published, or disclosed to others without written authorization from Apple Inc.

Primary Outcome	Atrial fibrillation or atrial flutter of at least 30 seconds duration on an ambulatory ECG patch monitor.
Secondary Outcomes	1. Arrhythmias other than AF on an ambulatory ECG patch monitor 2. Self-reported contact with healthcare provider
Study Devices	Irregular Rhythm Notification feature ECG app
Duration of Study Participation	Enrollment will occur over approximately a 6 month-period. Every participant will complete baseline questionnaires and wear an ambulatory ECG patch for up to 7 days. Every participant will receive an app notification to complete a web-based Patient Reported Outcomes (PRO) survey 15 and 60 days following enrollment. Participation in the study will end after completion of the 60 day PRO survey or after 90 days, whichever date is earlier.
Number of Participants	Approximately 2600 participants will be enrolled

This document contains information that is privileged or confidential and may not be disclosed unless such disclosure is required by applicable laws and regulations. The information in this document is the property of Apple Inc. and may not be reproduced, published, or disclosed to others without written authorization from Apple Inc.

1.1 INTRODUCTION

1.1 Background

Undiagnosed Atrial Fibrillation

Atrial fibrillation and atrial flutter (AF) affect approximately 6 million people in the US, with prevalence expected to rise to 12 million by 2030 (Benjamin 2018). AF is associated with higher rates of stroke, heart failure, thromboembolic events, cognitive decline, and death (Benjamin 2018). However, approximately 13% of AF is estimated to be undiagnosed ([name] 2018). There is a need to identify new strategies to identify these individuals to connect them with appropriate treatments to prevent stroke and modify risk factors.

Guidelines for AF Screening

The USPSTF recently published an “I” recommendation for AF screening in asymptomatic individuals, finding that there was insufficient evidence to recommend for or against screening for AF (USPSTF 2018, Jonas 2018). Specifically, there was insufficient evidence on whether screening for asymptomatic AF improves health outcomes compared to usual care. Additionally, potential harms of screening were not well-characterized.

Wearable Health Technology

Wearable health technologies offer a novel approach for disease screening. Users wear devices on a daily basis, and there is an opportunity to screen for AF passively and actively in the moment when an individual has symptoms. This approach may be able to identify more individuals with AF. Virtual care models may be able to connect these individuals with treatment. Additionally, wearable technology may be able to facilitate monitoring of disease and management of risk factors (Chen 2018).

Irregular Rhythm Notification (IRN)

The Irregular Rhythm Notification (IRN) feature is a software-only mobile medical application that is intended to be used with the Apple Watch. The feature analyzes pulse rate data to identify episodes of irregular heart rhythms suggestive of AFib. Using observable variations in PPG signal intensity, changes in blood flow can be measured and beat-to-beat pulse measurements can be made. During normal sinus rhythm, there is minimal variation in pulse. However, during AF, the beat-to-beat variability increases significantly. Therefore, a PPG signal can be used to differentiate between a regular pulse and an irregular pulse that may be indicative of AF.

An algorithm has been developed by Apple to identify periods of irregular pulse based on PPG signal variation as measured by the Irregular Pulse Notification Algorithm (IPNA). The time between PPG signal peaks observed during periods of minimal arm movement are marked as intervals between heart beats. A tachogram is a period of time over which heart beat intervals

This document contains information that is privileged or confidential and may not be disclosed unless such disclosure is required by applicable laws and regulations. The information in this document is the property of Apple Inc. and may not be reproduced, published, or disclosed to others without written authorization from Apple Inc.

are measured. The degree of beat-to-beat variability is measured from spot tachograms over the course of approximately one minute intervals. An irregular tachogram is flagged when the variability, measured using a Poincare plot, crosses a predefined threshold. An IPNA checks multiple tachograms over a period of approximately an hour or more. An IRN is then sent to the user when a period of an irregular pulse suggestive of AFib has been identified. This feature was granted FDA de novo classification on 9/11/2018.

ECG app

The ECG app is a software-only mobile medical application intended for use with the Apple Watch to create, record, store, transfer, and display a single channel ECG similar to a Lead I ECG. The ECG app processes electrical signals from two sensors on the Apple Watch - an electrode on the back of Apple Watch and an electrode on the digital crown. A user opens the ECG app on their Apple Watch, places a finger on the digital crown, and remains still for 30 seconds to capture an ECG. The ECG app analyzes the waveform to determine the presence of atrial fibrillation (AFib) or sinus rhythm on a classifiable waveform. The ECG app waveform is stored in the Health App and can be exported as a .pdf. This app was granted FDA de novo classification on 9/11/2018.

1.2 Study Rationale

The IRN feature and ECG app will be available to the public as a software update in early December 2018. IRN will be available on Apple Watch Series 1-4; ECG app will be available on Apple Watch Series 4.

The data collected in this study will provide an understanding of the experience of participating users of IRN and ECG app to help inform how mobile medical applications, such as the IRN and ECG app may be optimally used to facilitate heart disease screening and treatment. Findings may also help to inform the design of future research to determine whether use of Apple Watch to facilitate novel approaches to heart disease screening and treatment can improve health outcomes.

This document contains information that is privileged or confidential and may not be disclosed unless such disclosure is required by applicable laws and regulations. The information in this document is the property of Apple Inc. and may not be reproduced, published, or disclosed to others without written authorization from Apple Inc.

2.0 STUDY OBJECTIVES

2.1 Research Question

The overall objective is to characterize the ability of Apple Watch rhythm analysis software to identify AF and facilitate subsequent clinical evaluation among users who contact AppleCare.

2.2 Study Objectives

1a. To measure the proportion of participants with an Irregular Rhythm Notification (IRN) prior to enrollment who have atrial fibrillation or atrial flutter (AF) confirmed by ambulatory electrocardiographic (ECG) patch monitoring.

1b. To measure the proportion of participants with an ECG app classification of Atrial Fibrillation (ECG app-AFib) prior to enrollment who have AF confirmed by ambulatory ECG patch monitoring.

2a. To measure the proportion of participants who receive an IRN or ECG app-AFib reporting contact with a non-study healthcare provider at 15 and 60 days after study enrollment.

2b. To measure the proportion of participants with an ECG app classification of inconclusive prior to enrollment who have AF confirmed by ambulatory ECG patch monitoring.

2c. To measure the proportion of participants who have AF confirmed by ambulatory ECG patch monitoring by age at enrollment (< 65 and 65+).

This document contains information that is privileged or confidential and may not be disclosed unless such disclosure is required by applicable laws and regulations. The information in this document is the property of Apple Inc. and may not be reproduced, published, or disclosed to others without written authorization from Apple Inc.

3.0 OUTCOMES

3.1 Primary Outcome

Atrial fibrillation or atrial flutter of at least 30 seconds duration on an ambulatory ECG patch monitor.

3.2 Secondary Outcomes

1. Arrhythmias other than AF on an ambulatory ECG patch monitor
2. Self-reported contact with healthcare provider

This document contains information that is privileged or confidential and may not be disclosed unless such disclosure is required by applicable laws and regulations. The information in this document is the property of Apple Inc. and may not be reproduced, published, or disclosed to others without written authorization from Apple Inc.

4.0 STUDY DESIGN

4.1 Overall Study Design

Scope

This will be a prospective, single arm, experimental non-significant risk study, conducted with the assistance of eligible participants.

Participants calling into AppleCare self-reporting that they have received an IRN or ECG app classification of AF or inconclusive (defined as “Inconclusive,” “Heart Rate Over 120,” or “Heart Rate Under 50”) will be offered information about participation in the study, and the AppleCare representative will offer to e-mail the participants a link to download the Study App for more information. If the participant agrees, the participant will be emailed a link to download the Study App. Once downloaded, the Study App will provide the information about the study and screen for eligibility. If the participant meets the eligibility criteria and wishes to enroll in the study, the Study App will initiate the consenting process and provide the consent and authorization to sign in the app. Participants who install the Apple Heart Study 1.2 App and meet the eligibility criteria proceed to consent and then be enrolled in the study.

Participants will be required to provide signed informed consent; once enrolled they will complete a short questionnaire to collect demographic information, medical history, and health status, after which the study period will commence.

Monitoring

After enrollment in the study, participants will be prompted to contact the telemedicine technology services company, American Well Corporation (together with the Online Care Group, the "Study Telehealth Provider") to conduct Study Telehealth Visit #1 (voice or video). During Study Telehealth Visit #1, participants will undergo a virtual medical evaluation which will include an abbreviated assessment for symptoms, medical history, and medications.

Participants with urgent symptoms (chest pain, shortness of breath, fainting/losing consciousness) will be directed to an urgent care clinic or emergency room for medical evaluation. For participants with non-urgent symptoms, the Study Telehealth Provider will order an ambulatory ECG monitor (i.e. an ePatch) from BioTelemetry. Participants will be expected to contact the Study Telehealth Provider within 30 days of enrollment. Study participants will be reminded to initiate Study Visit #1 with reminders via email and phone calls if needed. Participants who call after 30 days will still be able to obtain an ePatch and undergo remaining study procedures, but may not be included in all analyses.

The participants will be mailed the ambulatory ECG monitor, which the participant will then be requested to wear for up to 7 days. The minimum analyzable time acceptable for primary

This document contains information that is privileged or confidential and may not be disclosed unless such disclosure is required by applicable laws and regulations. The information in this document is the property of Apple Inc. and may not be reproduced, published, or disclosed to others without written authorization from Apple Inc.

analysis is one hour. Participants with the ECG app will be asked to take an ECG app recording at least 2 times each day while wearing the ePatch, as well as after receiving an irregular rhythm notification. The participant will then mail the ambulatory ECG monitor back to BioTelemetry, which will generate a standard technical report that will be read by BioTelemetry's technical readers. The report will be adjudicated by two board-certified clinicians, and a final report will be made available to the Study Telehealth Provider by BioTelemetry.

A second study visit, Study Visit #2, will occur with the Study Telehealth Provider once the ambulatory ECG monitor results are available. After the final ambulatory ECG monitor report is made available to the Study Telehealth Provider, the Study Telehealth Provider will contact the participant to prompt them to complete Study Visit #2. During Study Visit #2 (voice or video), the ambulatory ECG monitor results will be reviewed. If AF or any other arrhythmias have been detected in reviewing the ambulatory ECG monitor data, or if there are other non-urgent symptoms needing further evaluation, the Study Telehealth Provider will direct the participant to their primary health care provider, or other health care provider as deemed appropriate by the Study Telehealth Provider. The report and visit summary will be made available to the participant and also to participant's physician or health care provider, if the participant provides his/her physician information and permission to send that physician a copy of the report. For participants who do not have an established primary health care provider, the Study Telehealth Provider will encourage and offer advice in establishing a primary care provider per standard Study Telehealth Provider protocol.

Patient Reported Outcomes (PROs)

Fifteen and sixty days after enrollment, participants will receive a separate app notification to complete the patient reported outcomes (PRO) questionnaires. The participant will be notified about the sixty day questionnaire even if the participant does not complete the fifteen day questionnaire. These outcomes will include whether or not the participant contacted a primary health care provider and what additional treatments or diagnostic tests they underwent. They will also be asked questions related to measures of anxiety about testing, experience with the IRN feature and ECG app, and health status. Participants will receive reminders via notifications from the app to complete the PROs prior to the due date (within 30 days of notification).

This document contains information that is privileged or confidential and may not be disclosed unless such disclosure is required by applicable laws and regulations. The information in this document is the property of Apple Inc. and may not be reproduced, published, or disclosed to others without written authorization from Apple Inc.

5.0 STUDY POPULATION

5.1 Inclusion Criteria

1. Possession of the following at time of eligibility screening, ascertained from automatic hardware/software/device pairing check:
 - I. iPhone (5s or later) with iOS version 12.1.1 or later defined as iPhone model/iOS version used to complete screening eligibility.
 - II. Apple Watch (Series 1-4) with watchOS version 5.1.2 or later defined as Apple Watch model/watchOS paired with iPhone used to complete screening eligibility.
2. At least one of the following by self-report before consent:
 - I. Irregular Rhythm Notification
 - II. ECG app classification of Atrial Fibrillation
 - III. ECG app classification of Inconclusive defined as “Inconclusive,” “Heart Rate Over 120,” or “Heart Rate Under 50”
3. Age \geq 22 years at time of eligibility screening, ascertained from self-reported date of birth.
4. Current resident of the United States at time of eligibility screening, defined by self-reported state of residence within the 50 states of the United States or District of Columbia, and will reside in the United States for the length of the study.
5. Proficient in written and spoken English, defined by self-report of comfort reading, writing, and speaking English on iPhone.
6. Valid phone number associated with iPhone, ascertained from self-report.
7. Valid email address, ascertained from self-report.

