7.3.2 Study Telehealth Provider Visit #1

The Study App will provide a button for the participant to connect with the Study Telehealth Provider. The first connection with the Study Telehealth Provider will constitute Study Visit #1.

After the participant connects with the Study Telehealth Provider team, they will undergo a study visit. The participant will be asked about cardiovascular clinical signs and symptoms. If the Study Telehealth Provider concludes that the participant has a medical emergency, the Study Telehealth Provider will follow its emergency protocol and either instruct the participant and/or a family member, if available, to call emergency medical services (EMS) or will call on the participant's behalf if the participant and/or a family member are unable to contact EMS. Participants with a medical emergency will not be prescribed an ePatch.

Once emergency symptoms have been ruled out, the telehealth clinician will perform an abbreviated review of medical history and perform a virtual review of physical symptoms. The telehealth provider will also confirm which of the following the participant received: Irregular

This document contains information that is privileged or confidential and may not be disclosed unless such disclosure is required by applicable laws and regulations. The information in this document is the property of Apple Inc. and may not be reproduced, published, or disclosed to others without written authorization from Apple Inc.

Rhythm Notification, ECG app classification of AF, or ECG app classification of inconclusive. If the participant cannot confirm having received any of the above notifications or classifications, the Study Telehealth Provider will not prescribe an ePatch. The information obtained will assure that the Study Telehealth Provider Data Collection variables [see 7.3.3 Study Telehealth Provider Data Collection] are obtained.

The visit summary will be made available to the participant and also to participant's physician or health care provider, if the participant provides the Study Telehealth Provider information of participant's physician and permission to send that physician a copy of the report. Any referral visits will be conducted outside of the study, at the discretion of the participant, and at the cost of the participant.

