7.12 Participants that may be excluded from specific analyses

Participants may be excluded from some analyses for incomplete data or for various other reasons. The reasons may include:

1. Failure to contact Study Telehealth Provider within 30 days of enrollment.
2. Failure to be deemed eligible for ePatch wear due to emergent symptoms, determined at Study Visit #1.
3. Failure to return an ePatch within 45 days of enrollment.
4. Failure to begin wearing ePatch within 14 days of patch shipment
5. Failure to verify at Study Visit #1 that the participant had a cohort classification as either (1) Irregular Rhythm Notification, or status of (2) Afib or (3) Inconclusive via the ECG app (i.e., with at least 1 ECG recorded within the 14 days before study enrollment indicating classification of either AFib or Inconclusive, where the latter is defined as “Inconclusive,” “Heart Rate Over 120,” or “Heart Rate Under 50”)
6. Withdrawal from the study per Section 9.0

This document contains information that is privileged or confidential and may not be disclosed unless such disclosure is required by applicable laws and regulations. The information in this document is the property of Apple Inc. and may not be reproduced, published, or disclosed to others without written authorization from Apple Inc.

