1.2 Study design

This will be a prospective, single arm, experimental, non-significant risk study conducted with the assistance of eligible participants wearing an Apple Watch Series 1-4 with the IRN feature or an Apple Watch Series 4 with the ECG app who receive an IRN or an ECG app classification of AF or “inconclusive”.

The Irregular Rhythm Notification (IRN) feature is a software-only mobile medical application that analyzes pulse rate data to identify episodes of irregular heart rhythms suggestive of AFib. Using observable variations in photoplethysmogram (PPG) signal intensity, changes in blood flow can be measured and beat-to-beat pulse measurements can be made. During normal sinus rhythm, there is minimal variation in pulse. However, during AF, the beat-to-beat variability increases significantly. Therefore, a PPG signal can be used to differentiate between a regular pulse and an irregular pulse that may be indicative of AF.

An algorithm has been developed by Apple to identify periods of irregular pulse based on PPG signal variation as measured by the Irregular Pulse Notification Algorithm (IPNA). The time between PPG signal peaks observed during periods of minimal arm movement are marked as intervals between heart beats. A tachogram is a period of time over which heart beat intervals are measured. The degree of beat-to-beat variability is measured from spot tachograms over the course of approximately one minute intervals. An irregular tachogram is flagged when the variability, measured using a Poincare plot, crosses a predefined threshold. An IPNA checks multiple tachograms over a period of approximately an hour or more. An IRN is then sent to the user when a period of an irregular pulse suggestive of AFib has been identified.

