- **Missing Data Bias:** For some participants, the IRN or ECG app-AFib classification will occur but no subsequent analyzable ECG monitoring data will be available (e.g., participant requires urgent care, participant doesn't return patch). Because these participants will not provide ambulatory ECG monitoring data, they will not be included in analyses to estimate the proportions in Objectives 1a, 1b, 2b and 2c. Their exclusion may bias the estimates up or down. Participants who require urgent care are presumably more likely to have AF and their exclusion would lead to an underestimate. On the other hand, participants who do not return patch may be less sick and their exclusion would result in an overestimate of the proportion of participants with AF. This bias is an inherent limitation of an observational study.
- **Observation Period Bias:** It is possible that participants may receive an IRN or ECG app-AFib classification but the subsequent ECG monitoring may not be of sufficient length to observe AF.
- **Classification self-report bias:** For the primary analysis patients will be analyzed according to their self-reported classification status at enrollment. However, a change in data collection in Phase II of the study will allow tachogram data prior to patient enrollment to be used to validate the patient self-reported classification. Sub-group analysis will be performed using Phase II data where classifications will be validated

according to tachogram data and results compared between those who are in agreement with those who are not.

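### An ECG app result is accepted on self-report without the Series 4 watch that alone runs the app, so the 1b and 2b denominators can hold participants whose paired watch could not have produced it

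*Combined protocol and SAP*

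**What the plan says.** - **Watch model.** Protocol 5.1, criterion 1.II, admits "Apple Watch (Series 1-4) with watchOS version 5.1.2 or later". The Study App reads the model through the pairing check.
- **Qualifying result.** Criterion 2 requires "At least one of the following by self-report before consent": an IRN, an ECG app result of AFib, or an ECG app result counted as inconclusive. No watch model is attached to any of the three.
- **Which watch can produce what.** Protocol 1.2: "IRN will be available on Apple Watch Series 1-4; ECG app will be available on Apple Watch Series 4". SAP 1.2 describes the population as "wearing an Apple Watch Series 1-4 with the IRN feature or an Apple Watch Series 4 with the ECG app". That is a description; no eligibility or analysis rule repeats it.
- **Visit #1.** Protocol 7.3.2 has the provider ask which result was received, and then: "If the participant cannot confirm having received any of the above notifications or classifications, the Study Telehealth Provider will not prescribe an ePatch". The answer is recorded (7.3.3, item 2).
- **Failure to verify.** Protocol 7.12 item 5, which begins "Failure to verify at Study Visit #1 that the participant had a cohort classification as either (1) Irregular Rhythm Notification" and goes on to the two ECG app classes, lists this as a possible analysis exclusion. SAP Section 3 makes it a reason for the Fallout Subgroup, which is outside the EAS.
- **Cohort used for analysis.** Protocol 10.1 fixes cohort status at enrollment. SAP 4.7: "For the primary analysis patients will be analyzed according to their self-reported classification status at enrollment". The same item acknowledges self-report bias and plans a Phase II subgroup comparison.

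**The concern.** Objectives 1a, 1b and 2b are each conditional on which feature produced the result. An owner of a Series 1-3 watch who received an IRN and reports an ECG app result, whether from confusion between the two features or for another reason, meets the criteria as written. That person is then counted in 1b or 2b, and the AF yield attributed to the ECG app includes someone whose paired watch cannot run it.

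A second route does not depend on the watch model. Visit #1 asks for any one confirmed result. A participant who reported two and can confirm one keeps both cohort labels, because no section uses the recorded Visit #1 answer to change a label. This can place unconfirmed members in 1a as well as in 1b and 2b.

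**Working it through.** **1. The yardstick.** The only design figure that rests on these denominators is the interval width in protocol 10.5 and SAP 1.3. Wald width = 2 × 1.96 × √(p(1−p)/n) at p = 0.5:

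| n | Computed | SAP 1.3 |
|---|---|---|
| 400 | 0.0980 | no greater than 0.10 |
| 300 | 0.1132 | 11.3% |
| 200 | 0.1386 | 13.9% |

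The plan's figures reproduce. The half-width at 400 is about 4.9 percentage points.

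**2. What each denominator can contain**, setting protocol 1.2 against 5.1 and 7.3.2:

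| Objective | Result needed | Watches able to give it | Member whose paired watch cannot give it? | Member who confirmed only a different result? |
|---|---|---|---|---|
| 1a | IRN | Series 1-4 | No | Yes |
| 1b | ECG app AFib | Series 4 | Yes | Yes |
| 2b | ECG app inconclusive | Series 4 | Yes | Yes |

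**3. Three participants followed through the text.**
- *Series 2, true IRN, also reports ECG app AFib.* Passes 1.II and 2. Confirms the IRN at Visit #1, so a patch is ordered. With a timely patch and an hour of data, enters the EAS and, by self-report, both 1a and 1b.
- *Series 4, reports IRN and ECG app AFib, confirms only the second.* Gets a patch and stays in 1a.
- *Confirms nothing.* Gets no patch, joins the Fallout Subgroup and leaves the EAS. This route is already closed.

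**4. Size.** Let m be the share of a denominator wrongly in the cohort, p the AF proportion in true members and q that in the misplaced members. Observed proportion = (1−m)p + mq, so the shift is m × (q − p). The documents give none of m, p or q; all values below are assumptions.

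| m | q − p (points) | Shift (points) |
|---|---|---|
| 5% | −10 | 0.05 × −10 = −0.5 |
| 10% | −10 | 0.10 × −10 = −1.0 |
| 5% | −30 | 0.05 × −30 = −1.5 |
| 10% | −30 | 0.10 × −30 = −3.0 |
| 10% | +10 | 0.10 × +10 = +1.0 |

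For the Series 2 owner with a true IRN, q is the yield in IRN recipients. The gap to p is then the difference between the 1a and 1b yields, which may be small and could have either sign.

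**5. Precision cost of removing misplaced members.** From 400, removing 5% leaves 380 (worst-case Wald width 0.1005); removing 10% leaves 360 (0.1033).

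**6. Does the planned check cover this?** SAP 4.7 would validate self-report with tachograms from before enrollment. SAP 1.2 describes a tachogram as derived from the optical pulse signal, so it can bear on an IRN but cannot show that an ECG app result occurred. Protocol 7.9 collects retrospectively only the IRNs and ECG app classifications of the 14 days before consent; tachograms fall under prospective Phase 2 collection. Phase 1 collects no device data. The 14-day look-back does match the window protocol 10.1 uses for the ECG app cohorts, so better data for the check are already planned.

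**The case against.** The case for leaving the plan alone has substance. The SAP names the bias openly and plans to compare participants whose self-report is validated with those whose is not. Phase 1 ends around January 2019 and enrollment lasts about six months from a December 2018 release, so most participants would probably have Phase 2 data. Callers first describe the result to a trained AppleCare advisor. The app screens are separate study documents, and a branch on watch model may exist there unseen. A participant may also have recorded the ECG on a different Series 4 watch.

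What stands: the problem is narrower than the criteria alone suggest, and its frequency cannot be judged. What does not: neither the planned subgroup nor Visit #1 alters the primary estimate, and tachograms cannot check an ECG app result. If the app already branches on watch model, the protocol should say so.

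Four stronger readings are tempting but unsupported:
- *That 1a holds members whose watch could not have given the result.* IRN runs on every admitted series; 1a can hold only unconfirmed members.
- *That the denominators do contain such people.* The documents give no watch mix and no misreport rate. They can contain them.
- *That the unsure option in SAP Table 2 leaves some participants in the EAS but in no cohort.* Criterion 2 already required one of the three results before consent, and nothing says the later questionnaire overrides it.
- *That false overlap undermines the sample size.* It could shrink the exclusive IRN count and feed the 50% overlap trigger in 10.5. But the 1a denominator is everyone in the EAS with an IRN, exclusive or not, and 50% overlap is already allowed for.

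**Conclusion.** The point holds in limited form. As written, the plan can place Series 1-3 owners in the 1b and 2b denominators on an ECG app result their paired watch could not give. It can also keep participants in 1a, 1b or 2b on a result they did not confirm at Visit #1. Those with no verifiable result are already excluded.

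The illustrative effect on 1b is a fall of 0.5-3 points against a half-width of about 5, resting wholly on assumed values (m 5-10%, q 10-30 points below p). It is negligible if q is close to p and reverses if q exceeds p. This does not invalidate the primary estimates. It merits a change because the app already reads the field that closes the first route, and the data for examining the second are already to be collected.

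**What to change.** 1. **Study App and protocol 5.1.** Offer criteria 2.II and 2.III only when the pairing check finds a Series 4 watch.
2. **SAP 4.3.** Exclude from the 1b and 2b denominators anyone already enrolled with a Series 1-3 pairing, and report how many. They remain in 1a if they reported an IRN.
3. **Primary definition.** Otherwise keep self-report at enrollment. Replacing it with the Visit #1 answer would substitute a later oral report, expected up to 30 days after enrollment, for an earlier self-report. That is a trade-off, so it belongs in a sensitivity analysis.
4. **Sensitivity analysis of 1a, 1b and 2b.** Prespecify a repeat limited to participants whose specific result was confirmed at Visit #1 (7.3.3, item 2) or, in Phase 2, appears in the IRNs and ECG app classifications from the 14-day look-back in protocol 7.9. Amend SAP 4.7 to name those records instead of tachograms alone. An IRN older than 14 days would not appear, so a missing record should not count as disproof.

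**Cost.** One app condition on a field already read, and one or two SAP paragraphs. A few users who recorded the ECG on another Series 4 watch would be lost from the ECG app cohorts. The loss of precision is small, as shown above.
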